#### Figure 1 CONSORT flow diagram for ECoWeB-PROMOTE

#### Figure 2 CONSORT flow diagram for ECoWeB-PREVENT

#### 5.6 Adherence to intervention and personalised intervention components

Measures of intervention adherence for the active interventions will include the following.

- 1. Number of uses of the app
- 2. Percentage of relevant self-help package completed
- 3. Number of challenge tasks completed
- 4. Number of times the tools are practiced (in total across all tools and for each tool)
- 5. Number of days used (in total and longest streak of consecutive use)
- 6. Number of days that daily mood rating is completed (maximum of once per day)
- 7. Number of times that ecological momentary ratings are completed
- 8. Overall time spent on the app

For the usual care arm, intervention adherence will include level of self-monitoring via the app. Adherence measures will be reported descriptively by trial arm (Table A2). For the personalised active intervention we will report the numbers of participants who receive each of the four components (achievement appraisal, social appraisal, rumination, emotion knowledge and perception), and also the numbers of participants who receive each of the six possible combinations of two of the four components (Table A.3).

## 6. Statistical analysis

#### 6.1 Trial outcomes

All trial outcomes will be collected for both PROMOTE and PREVENT; the only difference between the trials in terms of outcome variables is in the choice of primary outcome measures. For PROMOTE, the primary outcome measure is WEMWBS, whereas for PREVENT the primary outcome measure is PHQ-9.

Outcomes for PROMOTE and PREVENT include

- 1. WEMWBS (primary outcome measure for PROMOTE)
- 2. PHQ-9 (primary outcome measure for PREVENT)
- 3. WSAS
- 4. GAD-7
- 5. EQ5D-3L
- 6. ADSUS-adapted (health economic evaluation)
- 7. MINI-IPIP-N

Full details of these outcomes are set out in the Data Management Plan (more specifically Data Dictionary appendix), including the following items.

- 1. Full name of outcome measure
- 2. Abbreviation
- 3. Description of what is being measured
- 4. Type of measure: screening, outcome, mechanistic
- 5. Directionality (high scores indicate more positive or negative outcome)
- 6. Number of items
- 7. Item ranges

- 8. Overall score ranges
- 9. Subscales with number of items, item numbers, range
- 10. Item numbers for items that require reverse coding (i.e. the meaning of the item is expressed in the opposite direction from the overall scale)
- 11. Guidelines to address individual item missingness
- 12. MCID (if available)
- 13. Metric used for calculation (e.g. mean, total, percentage, algorithm)

All outcomes are questionnaire based continuous measures. The primary follow-up timepoint is 3 months, therefore the primary outcome for PROMOTE is WEMWBS at 3-month follow-up, for PREVENT the primary outcome is PHQ-9 at 3-month follow-up.

For ease of interpretation, all continuous outcomes will be reported using the directionality of higher scores indicating a more positive outcome. Therefore, some scales will be reversed by comparison to their standard usage (see the Data Management Plan for more details on outcome variables and their scoring procedures).

For each follow-up timepoint, there will be an initial email sent to the participant to request outcome data, followed by a reminder after 7 days. The link to submit outcome data will expire after 2 weeks following the reminder, resulting in a time window for data collection of just under 3 weeks. It is possible that some data collection may occur outside the time window, e.g. data collected by telephone.

#### 6.1.1 Derived variables

For the primary outcome in each trial we will create binary outcomes to indicate whether the participant (i) had an improvement  $\geq$ MCID from baseline and (ii) had a deterioration  $\geq$ MCID from baseline. These outcomes will be included in the inferential analyses for the ITT population using observed data only.

## 6.2 Purpose of the analyses

The purposes of the statistical analyses are as follows:

- 1. to provide descriptive baseline data by trial arm;
- 2. to report attrition at all follow-up timepoints;
- 3. to report individual outcome missingness at all follow-up timepoints;
- 4. to report adherence to the intervention in the active treatment arms;
- 5. to evaluate effectiveness of the active interventions relative to control, and the personalised active intervention relative to the standard active intervention, using inferential analyses;
- 6. to perform additional analyses to investigate potential moderators of the intervention effect; and
- 7. to provide descriptive data on serious adverse events.

Details of the quantitative mediation analyses will be described in a separate mediation analysis plan.

## 6.3 Analysis methods

All continuous outcomes will be reported descriptively (mean, SD) at all follow-up timepoints. Inferential analyses The primary analyses for the primary and continuous secondary outcomes will use linear regression models with adjustment for baseline score, age (as a continuous variable rather than the dichotomised minimisation variable), country, and any other participant characteristics observed at baseline to be unbalanced across treatment arms (meeting the criteria set out in Section 5.5). The primary follow-up time will be at 3 months; analysis of 12-month follow-up data will also be performed using the same approach. The primary analyses will be based on an intention to treat (ITT) approach (i.e. all participants will be included in the analyses according to their randomised allocation) and will use observed data only.

As a secondary analysis, we will perform repeated measures analyses (using a mixed effects linear regression model with a random effect on participant) for primary and secondary continuous outcomes, including data from participants with observed data for at least one of the three follow-up timepoints. Analyses will be performed to compare both active interventions with usual care, and to compare the personalised active intervention with the standard active intervention. A fixed effect interaction between timepoint and trial arm will be used to evaluate differential treatment effects across timepoints. Adjustments for baseline covariates will be made as for the primary analysis regression models; baseline score will be included as a covariate. Binary outcome measures will be analysed using logistic regression models with adjustments for covariates as above.

The primary analyses will use only the data collected during the time window. The amount of such data will be determined, with the possibility of performing a sensitivity analysis should the amount of data collected outside the time window be substantive. These analyses will be performed using observed data for the ITT population (i.e. according to initial random allocation). No formal adjustments of p-values for multiple testing will be performed; the results for the primary outcome will be interpreted first and the results of the secondary outcomes will then be interpreted in the light of multiple testing. The results of all descriptive and inferential analyses for the primary and secondary continuous outcomes are set out in Tables A.4–A.10.

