7.3.1 Method of implementing the randomisation/allocation sequence

Participants will be randomised by a custom-built web service which interfaces with the EXCTU database. This will be an automated process. The EXCTU database will send MSS the email address and the version of the App that the participant is randomised to. The participant will automatically be set up with an MSS account and this account number will be recorded and linked to the trial number. Once the MSS account has been set up, the participant will receive an automated email from MSS providing instructions on how to access their version of the App. In the unlikely case that it is necessary, site researchers will be able to log on to the EXCTU website to identify which condition the participant has been allocated so that they can give advice on any problems the participant has in using the App. If this happens then this will be logged as an unblinding. The functioning of the randomisation programme will be checked by the data team and reported to the DMEC.

Detailed procedure for randomisation

- 1. Participants are allocated to one of 2 trials within the cohort:
 - a. ECoWeB-PROMOTE (EC profile indicates low risk for emotional difficulties),
 - b. ECoWeB-PREVENT (EC profile indicates higher risk for emotional difficulties)

For each trial, participants are randomised on a 1:1:1 basis into the 3 arms on an intentionto-treat basis: usual practice plus offered personalized digital EC self-help (the experimental intervention), usual practice plus offered digital CBT self-help (active control) and continuing with usual practice including self-monitoring app (control). Gender, age and country are used for minimisation.

- 2. The system must record the allocation and the date randomised.
- 3. The participant and researcher remain blind to the allocation.
- 4. If the participant is randomised to the EC condition (in any of the trials) then the EC profile from step 5 will be used to tell Monsenso which version of the App to provide the participant with.
- 5. An algorithm (simple set of rules) will be provided to determine the version of the app received within the personalised EC configuration and the bespoke website will communicate this information to Monsenso. This will be based on trial, interventions and EC category.
- 6. The system notifies Monsenso of the allocation. They will need to be notified of the version of the app, trial no, participant language and participant email address.

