10.3 Statistical analysis plan

A detailed statistical analysis plan (SAP) is to be produced; the main points of the statistical analysis are summarised here – for full details see project SAP whose details supercede this. The statistical analysis for each trial will follow the same broad guidelines; any adaptations for each trial individually we reported

in the detailed SAP. The SAP will be approved by the TSC prior to end of participant recruitment. Any amendments to the TSC will be documented and approved by the TSC on an ongoing basis.

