10.3.2 Primary analysis

The primary outcomes (WEMWBS (ECoWeB-PROMOTE); PHQ-9 (ECoWeB-PREVENT) and secondary outcomes will be compared at 3-month follow-up. The primary and secondary continuous outcomes will be reported descriptively (mean and standard deviation (SD)) and inferential comparisons will be reported between the three treatment contrasts ((1) usual practice plus personalised digital self-help EC vs. usual practice alone; (2) usual practice plus non-personalised automated digital CBT self-help vs. usual practice alone; (3) usual practice plus personalised digital self-help EC vs. usual practice alone; (3) usual practice plus personalised digital self-help EC vs. usual practice plus non-personalised automated digital CBT self-help) using linear modelling. All analyses will be based on an intention to treat principle (i.e. according to original allocation irrespective of intervention adherence) and will include participants with complete outcome data at 3-month follow-up, and will adjust for baseline outcome score (where relevant) and minimisation variables (age, gender, country). Furthermore, we will adjust for any baseline participant characteristics that are substantively unbalanced at baseline (defined as a difference ≥ 10 percentage points across categories for a categorical variable, or a difference in means >1 SD for continuous variables), and if the characteristic is thought to be predictive of outcome. Binary secondary outcomes (occurrence of major depressive disorder; generalized anxiety disorder) will be reported as proportions and analysed used logistic regression.

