#### 1.4 Statistical analysis plan and trial protocol

This SAP is not intended to be a standalone document and should be used in conjunction with the trial protocol (version 1.3 dated 05/07/2021).

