#### 3.3 Randomisation

Within both PROMOTE and PREVENT separately, participants will be allocated to one of the three interventions in a 1:1:1 ratio using a minimisation algorithm to promote balance across the arms overall and within minimisation factors. The minimisation factors to be used are gender (categorised as male:female:both:neither anticipated to be recruited in a 20:70:5:5 ratio), age (categorised as 16–17:18–22, anticipated to be recruited in a 20:80 ratio), and country of residence (UK:Germany:Spain:Belgium, anticipated to be recruited in a 28:28:28:18 ratio). The first 50 randomisations (for both trials) will be performed using simple randomisation; subsequent randomisations will use the minimisation algorithm, taking account of the previous allocations. Further details of the randomisation procedure are provided elsewhere (Trial selection, randomisation, selection of emotional competence intervention components document).

Randomisation across all countries will be carried out by ExeCTU. The randomisation algorithm will be automatically invoked when the participant has submitted the required baseline data and provided consent. The participant will be immediately informed of the allocated treatment and the downloaded version of the app will provide the appropriate intervention. There is no possibility for a participant to receive a version of the app other than the version to which the participant was randomly allocated.

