#### 6.4 Interactions between treatment and participant characteristics

To investigate differential treatment effects across subgroups of participants, we will perform a series of models, for the primary outcome only at 3-and 12-month follow-up, including an interaction term between treatment arm and the participant characteristic (as well as the other covariates to be adjusted for; each model will include one interaction term only). The participant characteristics to be investigated for differential treatment effects are age (continuous and dichotomised as for the minimisation algorithm), country and gender. The interaction terms will be reported as coefficients and 95% confidence intervals, with a global p-value (Table A.11). It is acknowledged that these analyses will have limited statistical power, and hence are exploratory in nature, and the results should be viewed with caution.

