#### 6.5 Missing data

Demographic characteristics of participants who do not provide data for the primary outcome measure of their trial at 3- and 12-month follow-up will be set out (including participants who have

formally withdrawn (but allowed their previously collected data to be used), and participants not formally withdrawn but did not complete the primary outcome at follow-up) (Tables A.12 and A.13).

Multiple imputation using chained equations (MICE) will be used to impute primary and secondary continuous outcomes. Predictive mean matching will be the method for imputing individual scores; the number of imputed datasets will be determined by the percentage of participants in each trial that have missing 3-month outcome data (i.e. WEMWBS for PREVENT, PHQ-9 for PROMOTE). Imputation models will be informed by treatment arm, baseline scores, other covariates to be included in the model (i.e. minimisation covariates), and other baseline characteristics found to predict outcome or propensity for missingness (logistic regression models will be used to investigate the associations between baseline characteristics and missingness). Regression models using the imputed datasets will be performed using the same methods as described in Section 6.3 for the ITT population (Tables A.4–A.10). Analyses using imputed data will be considered as a secondary analysis.

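### SAP 6.3 leaves gender, a minimisation factor, out of the primary model that Protocol 10.3.2 says adjusts for it; the effect is small and the correction is one word

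*SAP*

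**What the plan says.** SAP 6.3 gives the primary linear model "adjustment for baseline score, age (as a continuous variable rather than the dichotomised minimisation variable), country, and any other participant characteristics" found unbalanced under SAP 5.5. Gender is not named.

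Other places point the other way:

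- **SAP 3.3:** "The minimisation factors to be used are gender", followed by age and country.
- **Protocol 7.3.1:** "Gender, age and country are used for minimisation".
- **Protocol 10.3.2:** the analyses "will adjust for baseline outcome score (where relevant) and minimisation variables (age, gender, country").
- **SAP 6.5:** the imputation model draws on "other covariates to be included in the model (i.e. minimisation covariates"), which treats the minimisation factors as being in the analysis model. SAP 6.7 does the same when it adds a lockdown predictor, and SAP 8.16 adjusts the cost regressions for the minimisation variables.
- **SAP 6.4:** treatment interactions are fitted for "age (continuous and dichotomised as for the minimisation algorithm), country and gender".

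On precedence, Protocol 10.3 says "for full details see project SAP whose details supercede this". SAP 1.4 says the SAP "is not intended to be a standalone document and should be used in conjunction with the trial protocol".

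**The concern.** An analysis should normally adjust for the factors used to balance the allocation. Minimisation removes chance differences in gender between arms. A model that omits gender still counts the gender-related variance as noise, so its standard errors are a little too large.

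The second issue is that the primary model has two readings. SAP 6.3 explains its departure on age (continuous instead of dichotomised) but gives no reason for dropping gender. Because the SAP takes precedence, the shorter list governs if followed literally. The same list carries over to the 12-month, repeated-measures and logistic models (SAP 6.3), the regressions on imputed data (6.5), the CACE models (6.6) and the adverse-event models (6.10). The cost models in 8.16 would then contain gender while the primary clinical model would not.

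**Working it through.** **Inputs from the documents.** Two-sided alpha 0.05, 90% power and 40% attrition (Protocol 10.1). WEMWBS difference 3.0, SD 11.3 (10.1.1). PHQ-9 difference 2.59, SD 5.4 (10.1.2). Gender mix 20:70:5:5 (SAP 3.3). Revised total 3599 (SAP 6.9), split 70:30 (SAP 3.4).

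**Assumption.** Neither document gives a gender-outcome association. R² is the share of residual variance that gender explains after baseline score, age and country; it is taken as 1–5%.

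**1. Reproduce the plan's sizes.** n per arm = 2(1.960 + 1.282)² × SD²/difference².
- PROMOTE: 298.2, or 300 per arm with the t correction; 300/0.6 = 500, and 500 × 3 = 1500.
- PREVENT: 91.4, or 93 per arm with the t correction; 93/0.6 = 155, and 155 × 3 = 465.

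Both agree with the plan. The PHQ-9 figure of 5.9 printed in SAP 3.4 would give about 18 per arm, so 2.59 is used here.

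**2. Standard error and type I error when gender is omitted but exactly balanced.** SE inflation = 1/√(1−R²) − 1. Type I error = 2[1 − Φ(1.96/√(1−R²))].

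| R² | SE too large by | Type I error |
|---|---|---|
| 1% | 0.50% | 4.89% |
| 2% | 1.02% | 4.77% |
| 5% | 2.60% | 4.43% |

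**3. Power.** Let t = difference/(SD√(2/n)), with the planning SD taken as the residual SD without gender. Power without gender = Φ[(t − 1.96)/√(1−R²)]. Power with gender = Φ[t/√(1−R²) − 1.96].

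Revised sizes per arm: PROMOTE 0.70 × 3599/3 = 840 randomised, × 0.6 = 504 analysed. PREVENT 0.30 × 3599/3 = 360 randomised, × 0.6 = 216 analysed.

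| Trial, analysed per arm | t | Without gender (R² 1–5%) | With gender (R² 1–5%) |
|---|---|---|---|
| PROMOTE, 300 | 3.25 | 90.29–90.74% | 90.46–91.56% |
| PREVENT, 93 | 3.27 | 90.61–91.06% | 90.78–91.86% |
| PROMOTE, 504 | 4.21 | 98.83–98.96% | 98.86–99.10% |
| PREVENT, 216 | 4.98 | 99.88–99.90% | 99.89–99.92% |

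The gain is 0.2–0.8 points at the planning sizes. At the revised sizes it is at most 0.14 points in PROMOTE and about 0.02 in PREVENT. In confidence-interval width, omission is like losing R² × n people per arm: 5–25 of 504 and 2–11 of 216. That describes interval width, not power. At 300 per arm and R² 5%, actually losing 5% of participants from a gender-adjusted analysis would give 90.17%, whereas omitting gender gives 90.74%.

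**4. Could SAP 5.5 bring gender back?** Minimisation was simulated on gender, age and country, with the first 50 allocated at random and an assumed 0.7 or 0.9 probability of following the rule thereafter. The largest gender spread across arms was 2.9 points at 360 per arm and 1.0 point at 840 per arm. A separate simulation of 465 participants (assumed probability 0.8) never reached 10 points in 6,000 runs. Even if the trigger were met, SAP 5.5 leaves entry to judgement about prognostic value.

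**5. Type I error after attrition.** With 40% random loss, the model without gender had simulated type I error of about 4.7–5.1% (Monte Carlo error 0.2–0.3 points). Values just above 5% are noise.

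**6. Bias.** In the linear models there is none under randomisation unless loss depends jointly on arm and gender. As an illustration on assumed values, a 0.4 SD gender contrast and a 5-point gender difference between arms among those analysed shift the estimate by 0.4 × 0.05 = 0.02 SD, or 0.02 × 11.3 = 0.23 WEMWBS points against a target of 3.0.

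**The case against.** The strongest reply is that the intended model is already clear. SAP 6.5, 6.7 and 8.16 all speak of the minimisation covariates, SAP 1.4 requires reading alongside a protocol that names gender, and no SAP text says gender is excluded. On that view this is an editorial matter, with a power effect near zero at the revised sizes.

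Most of that is fair. The omission looks like a slip and the numerical effect is small. Three further points also stand:

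- An imputation model richer than the analysis model is ordinary practice, so gender appearing in the former alone does no harm.
- The interaction models in 6.4 would conventionally carry their own main effects, so 6.4 is weak evidence of a defect in 6.3.
- In the logistic models, leaving out a prognostic covariate changes the odds ratio being estimated, so the statement about bias applies to the linear models only.

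What does not stand is the claim that the other passages repair 6.3. They show that the SAP disagrees with itself on the covariates of its confirmatory model, and the precedence sentence in Protocol 10.3 points to the shorter list.

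**Conclusion.** The concern holds. Read literally, SAP 6.3 drops a factor that the trial allocates by and that the protocol says it adjusts for, without giving a reason. The size of the effect rests on the assumed R² of 1–5%; a weaker gender association would make it smaller still. The result is slightly wide confidence intervals and a mildly conservative test, not false positives. It is worth correcting because the primary model should have only one reading and the improvement is essentially free. It does not threaten the trial's conclusions.

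**What to change.** Before unblinding, insert gender between age and country in the SAP 6.3 covariate list. Keep the clause on unbalanced characteristics, which matches Protocol 10.3.2 and 10.3.3.

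Add one sentence on coding. Gender has four levels in SAP 3.3, and Protocol 7.3 says sex where 7.3.1 and the SAP say gender, so state that the variable used by the minimisation program is the one analysed. Pre-state when the *both* and *neither* levels will be merged in sparse binary or adverse-event models. At 5% each and the revised target, each level has about 42 randomised and 25 analysed per arm in PROMOTE (0.05 × 840 and 0.05 × 504), and about 18 and 11 in PREVENT (0.05 × 360 and 0.05 × 216).

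The cost is one word, one sentence and up to three degrees of freedom; no new data are needed. Timing matters because SAP 1.7 classes changes made after data scrutiny and unblinded interpretation as post hoc.

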## 3.8 Timing of outcome assessments

Follow-up timepoints are at 1-, 3- and 12-month follow-up (3-month follow-up is the primary timepoint). Each participant will have a scheduled follow-up date for each of the three follow-up timepoints, to be allocated on date of randomisation. Data collection will be sought within a 14-day window (within 7 days before or after the scheduled date) for 1-month follow-up. Data collection will be sought within a 28-day window (within 14 days before or after the scheduled date) for 3- and 12-month follow-up. Data collected outside this window will not be included in the primary analysis, although sensitivity analyses including all collected data will be performed.

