## 8.11 Measurement of outcomes

The EQ-5D-3L will be administered with the adapted ADSUS at baseline, 3 and 12-months

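### The secondary repeated-measures model has only a participant random effect, so its arm-by-time confidence intervals rest on equal variances and equal correlations across visits at 1, 3 and 12 months

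*SAP*

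**What the plan says.** SAP section 3.8 sets the schedule: "Follow-up timepoints are at 1-, 3- and 12-month follow-up". Section 6.3 then says "As a secondary analysis, we will perform repeated measures analyses", fitted "using a mixed effects linear regression model with a random effect on participant", for the primary outcome and the continuous secondary outcomes. Participants enter if they have data at one or more follow-up visits, and baseline score is a covariate. "A fixed effect interaction between timepoint and trial arm will be used to evaluate differential treatment effects across timepoints".

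Section 6.3 adds that the results "are set out in Tables A.4–A.10". Those shells show arm-by-time interaction coefficients at 3 and 12 months with 95% confidence intervals, taking usual care and the 1-month visit as references, and a global p-value. SAP section 4.1 assigns the global p-value to models with several contrasts and uses the confidence intervals to interpret each contrast.

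Neither document states a residual covariance structure, a random slope, robust standard errors or a fallback. Protocol section 10.3.3 says only that repeated measures analyses will be done.

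**The concern.** A participant random effect with independent residuals implies compound symmetry: one variance at all visits and one correlation for all pairs. The first two follow-ups are 2 months apart and the outer two are 11 months apart. With self-reported mood and well-being scores, the closer pair would usually be expected to correlate more strongly. The model would then estimate something near the average correlation and apply it to every contrast.

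This matters most for differences between visits, because their variance depends directly on the correlation between those two visits. The arm-by-time interactions are such differences, and they are what the repeated-measures rows of the tables report. Effects at all time points are a stated secondary objective in both trials (Protocol section 3.1). Timing matters too: under SAP sections 3.9 and 7.1 this analysis is run after the 12-month lock, when the statistician knows the allocations. A covariance structure left open now would be chosen unblinded.

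**Working it through.** The plan gives no figure for this model, so there is none to reproduce.

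**Inputs**
- Visits at 1, 3 and 12 months (SAP 3.8), so gaps of 2, 9 and 11 months.
- Model: participant random effect, arm-by-time interaction, 1 month as reference (SAP 6.3, Tables A.4 to A.10).
- Two-sided test at 0.05 (SAP 4.1, Protocol 10.1).
- Residual correlations after adjustment: not in the documents. Assumed, in the order 1-3, 3-12, 1-12 months.

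**Formulae (equal variances s², complete data, large sample)**
- True variance of a within-person difference between visits j and k: 2s²(1 − ρ_jk).
- Variance the model uses: 2s²(1 − ρ̄), where ρ̄ is the mean of the three correlations.
- Ratio of model SE to true SE: r = √[(1 − ρ̄)/(1 − ρ_jk)].
- Actual size of the nominal 5% test: 2[1 − Φ(1.96 r)].

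**Middle scenario, 0.60/0.42/0.35**
- ρ̄ = (0.60 + 0.42 + 0.35)/3 = 0.457.
- 12 v 1 month: r = √(0.543/0.65) = 0.914, size 7.3%.
- 3 v 1 month: r = √(0.543/0.40) = 1.165, size 2.2%.

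**All scenarios**

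| Assumed correlations | ρ̄ | 12 v 1: r, size | 3 v 1: r, size |
|---|---|---|---|
| equal, 0.50 | 0.500 | 1.00, 5.0% | 1.00, 5.0% |
| 0.55/0.45/0.40 | 0.467 | 0.943, 6.5% | 1.089, 3.3% |
| 0.60/0.42/0.35 | 0.457 | 0.914, 7.3% | 1.165, 2.2% |
| 0.65/0.38/0.30 | 0.443 | 0.892, 8.0% | 1.261, 1.3% |

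The 4-degree-of-freedom global interaction test keeps a size of about 5% to 6% in all of these, because the two errors run in opposite directions.

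**Sensitivity to dropout and variance.** This used a separate set of correlations, 0.60/0.50/0.45 to 0.70/0.40/0.25, comparing the model SE with the sandwich SE. Observed proportions were 75%, 60% and 50% at 1, 3 and 12 months. The 60% follows from the plan's 40% attrition; the other two are assumptions.
- Equal variances: 12 v 1 month 6.7% to 9.6%; 3 v 1 month 3.3% to 1.1%; global 5.3% to 6.6%.
- SD rising in the ratio 1/1.05/1.2 (assumed): 12 v 1 month 7.9% to 10.6%; 3 v 1 month 2.5% to 0.7%; global 6.3% to 7.6%.

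**After the change.** With an unstructured covariance or participant-clustered SEs, the large-sample ratio is 1.00 and the size 5% for each interaction. The random-intercept estimator's true SE is at most about 1.3% above the unstructured one, so the change corrects the stated intervals and barely alters precision.

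**The case against.** The best reply is that the SAP names a random effect but does not rule out a residual structure or robust standard errors alongside it. On that view the plan is under-specified, not wrong. That is fair as far as it goes. Still, the natural reading is a random intercept with independent residuals, and either reading calls for the same sentence.

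Second, the global p-value is close to nominal. This stands, but SAP section 4.1 interprets individual contrasts through their confidence intervals, and those are the quantities distorted. One interval too narrow and another too wide do not offset each other for a reader.

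Third, the reach is limited, and this stands in full. Section 6.3 says "The primary analyses for the primary and continuous secondary outcomes will use linear regression models with adjustment for baseline score", with the same single-visit approach at 12 months. Neither regression uses this model. EQ-5D-3L is also outside the point: "The EQ-5D-3L will be administered with the adapted ADSUS at baseline, 3 and 12-months". With two follow-up visits there is only one correlation, so equality is no constraint, even though the shells for Tables A.8 and A.9 carry 1-month columns.

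A reader might go further in three ways that the documents do not support:
- **That the 12-month treatment effect is tested at the wrong level.** The tables take that effect from its own regression; the repeated-measures rows report interactions only.
- **That the handling of missing data is compromised.** No bias has been shown, the efficiency loss is about 1.3% at most, and multiple imputation is planned separately (SAP 6.5).
- **That a common baseline slope biases the interactions.** Under randomisation it does not.

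**Conclusion.** The point holds as a conditional one about a secondary analysis. As written, the model assumes equal variances and equal correlations across unequally spaced visits. If correlation falls with the gap over the assumed range 0.55/0.45/0.40 to 0.65/0.38/0.30, with equal variances and complete data, the 12-versus-1-month interaction is tested at about 6.5% to 8.0% with an interval too narrow, and the 3-versus-1-month interaction at about 3.3% to 1.3% with an interval too wide.

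It would be wrong to conclude that the standard errors are in error as a matter of fact. Under equal variances and correlations they are correct, and the documents contain no correlation data to settle it. No primary conclusion depends on this model. It is worth changing because the assumption is unargued, the affected intervals will be reported for every outcome with three follow-up visits, and the remedy is nearly free.

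**What to change.** In SAP section 6.3, replace the participant random effect with an unstructured within-participant residual covariance over the three follow-up visits. Keep time categorical and interacted with arm, and fit by REML. In Stata this is `mixed` with no random intercept and `residuals(unstructured, t(visit))`. Name participant-clustered robust standard errors as the fallback if the model does not converge, using maximum likelihood if the software does not offer them with REML. State that the same specification applies to the repeated-measures sensitivity options in SAP section 6.9. A baseline-by-time term is optional.

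The cost is one or two sentences and no new data. Each trial estimates six covariance parameters per outcome (three variances, three covariances). That is feasible in both: PROMOTE plans 1500 participants, and even PREVENT's 465 leaves 0.60 × 465 = 279 at 3 months after the planned attrition. The change should be dated before anyone sees unblinded results, since SAP section 1.7 treats later revisions as post hoc.
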